2.2 Secondary Outcomes: Compared between treatment arms

- Incidence of worsening heart failure during hospitalization requiring IV inotropic therapy, new admission to an intensive care unit, new non-invasive positive pressure ventilation with bilevel positive airway pressure, or increase in the IV diuretic protocol intensity by 2 rows after Study Day 1 as adjudicated by the Clinical Event Committee
- Hospital readmission within 30 days of discharge for heart failure or diabetic reasons as adjudicated by the Clinical Event Committee
- 2.3 Exploratory Outcomes: Compared between treatment arms
 - NT-proBNP at discharge adjusted for baseline
 - Urine-output based Diuretic efficiency: 24-h total urine output (ml) per 40mg of IV furosemide equivalents on day 2 of IV diuretic therapy from 24-h urine collection (collected day 2-day 3)

- Fractional excretion of sodium (FENa)-based diuretic efficiency on day 2 of IV therapy: FENa per 40mg of IV furosemide equivalents of bolus loop dose using spot urine collected 2 hours after bolus loop dose
- Urinary Na/K ratio at day 2 of IV therapy adjusted for baseline
- Calculated 6-hour sodium output on day 2 of IV therapy using spot urine sodium collected 2 hours after bolus loop dose
- Increase in IV loop diuretic titration grid for urine output below the goal range
- Length of hospital stay, measured as days from admission to discharge
- Hospital admission within 30 days of discharge for any cause
- Number of days at home without hospitalization or emergency room visit during 30-day follow up period
- Presence of symptoms of congestion and dyspnea at discharge, measured via physical exam congestion scores¹⁵
 - Edema will be categorized as trace/mild (0 points), moderate (1 point), or severe (2 points).
 - Orthopnea will be characterized as present if the patient needed at least 2 pillows to breathe comfortably (2 points) or absent (0 points).
 - The Orthodema Score will be generated by the sum of the individual orthopnea and edema scores as in the table below:

Orthodema Score ¹⁵				
Mild edema	0	No congestion		
No orthopnea				
Moderate edema	1	Low-grade orthodema		
No orthopnea				
Severe edema or orthopnea	2			
Moderate edema and orthopnea		High-grade orthodema		
Severe edema and orthopnea	4			

Mild edema = below the knee with minimal denting Moderate edema = below the knee with significant pitting Severe edema = above the knee

- Mean Serum glucose during therapy
- Amount of total daily insulin doses (units) utilized per day during therapy among patients with type 2 diabetes, compared between treatment arms and to a prior to enrollment outpatient insulin regimen
- serum potassium covariate adjusted for baseline with attention to both elevation and depression

Single-Center Exploratory Outcomes at Vanderbilt University Medical Center

The following exploratory outcomes will only be performed in patients at Vanderbilt University Medical Center who elect to participate in a sub-study. Patients can decline to participate in this sub-study and still participate in parent clinical trial. To explore changes in the plasma proteome during IV diuresis, we will collect one 15mL blood sample (10mL in purple top EDTA tube and 5mL in red top tube) at baseline and on the final study day (Day 5 or discharge).

2.4 Safety Outcomes: Compared between treatment arms during the index stay from signing of informed consent to hospital discharge

- Change in the estimated Glomerular Filtration Rate by the MDRD equation at discharge adjusted for baseline
- Incidence of ketoacidosis, identified by the study team as elevated ketones in the urine and an arterial blood pH < 7.35 and adjudicated by the Clincal Events Committee
- Serum glucose covariate adjusted for baseline with attention to both elevation (> 400mg/dl) and depression (< 70mg/dl)
- Potential prolonged hospitalization as a result of hypoglycemia requiring medical intervention as adjudicated by the Clinical Events Committee
- Potential prolongation of hospitalization as a result of incidence of hypovolemic hypotension, defined as a symptomatic hypotension with a sustained systolic blood pressure less than 90 mmHg over 30 minutes and requiring medical intervention as adjudicated by the Clinical Events Committee. All hypotension episodes requiring medical intervention will be evaluated by the Clinical Events Committee.
- Inpatient mortality

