Exclusion Criteria	Type 1 diabetes Serum glucose < 80mg/dl at enrollment Systolic blood pressure < 90mmHg at enrollment Requirement of intravenous inotropic therapy at enrollment or anticipated need of therapy during the study period History of hypersensitivity to any SGLT2 inhibitors Women who are pregnant or breastfeeding Severe anemia (Hemoglobin < 7.5g/dl) Severe uncorrected aortic or mitral stenosis Inability to perform standing weights or measure urine output accurately History of diabetic ketoacidosis Chronic combination nephron blockade with loop and thiazide therapy as an outpatient scheduled daily for more than 7 days prior to admission (Does not include HCTZ < 50mg for blood pressure) Diffuse anasarca with 4+ edema and projected hypervolemia exceeding 40-pounds Severe hepatic impairment (Child-Pugh class C if severity of hepatic failure is in question) Clinical picture consistent with acute myocardial infarction including troponin elevation or ischemic changes on electrocardiogram Site investigator determines the subject is not a good candidate to participate in study at this time

Primary Endpoint	cumulative change in weight (kilograms) per 40mg of IV furosemide equivalents from enrollment to day 5 or discharge (if earlier) between protocolized diuretic therapy and dapagliflozin plus protocolized diuretic therapy guided by urine output			
Assessment Schedule (Appendix A)	Baseline : standing weight, NT-proBNP, BMP, hemoglobin A1c, spot urine values of sodium, potassium, and creatinine (calculate urine sodium/potassium ratio, FENa), vital signs, study loop diuretic and diabetic medication orders, congestion score, document baseline HF and diabetic medications, start urine output quantification, urine biobanking for future investigations including urinary exosomes.			
	Daily: standing weight, BMP, vital signs, urine output quantification, titration of study loop diuretic and diabetic medication orders, document HF and diabetic medications, adverse event assessment			
	Day 2 : daily assessments as above plus 2-hour post loop diuretic spot urine sodium, potassium, and creatinine. Calculate FENa, 6-hr sodium output, urine sodium/potassium ratio, 24-hour urine collection for quantification and diuretic efficiency calculation, urine biobanking for future investigations including urinary exosomes.			

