3.0 Inclusion/Exclusion criteria

- Inclusion Criteria
 - Age of 18 years or older
 - Randomized within 24 hours of presentation during a hospital admission for hypervolemic decompensated heart failure defined as either:
 - pulmonary artery catheterization with a pulmonary capillary wedge pressure greater than 19mmHg plus a systemic physical exam finding of hypervolemia (peripheral edema, ascites, or rales on auscultation)
 - in the absence of pulmonary artery catheterization data 2 of the following signs or symptoms: peripheral edema, ascites, jugular venous pressure > 10mmHg, orthopnea, paroxysmal nocturnal dyspnea, 5-pound weight gain, or signs of congestion on chest x-ray or lung ultrasound

- Standard-of-care monitoring on an inpatient ward and standard-of-care basic metabolic panel laboratory assessment once daily during the study period
- Planned or current use of IV loop diuretic therapy during current hospitalization
- eGFR \geq 25 ml/min/1.73m² by the MDRD equation
- Exclusion Criteria
 - Type 1 diabetes
 - Serum glucose < 80mg/dl at enrollment
 - Systolic blood pressure < 90mmHg at enrollment
 - Requirement of intravenous inotropic therapy at enrollment or anticipated need of therapy during the study period
 - History of hypersensitivity to any SGLT2 inhibitors
 - Women who are pregnant or breastfeeding
 - Severe anemia (Hemoglobin < 7.5g/dl)
 - Severe uncorrected aortic or mitral stenosis
 - Inability to perform standing weights or measure urine output accurately
 - History of diabetic ketoacidosis
 - Chronic combination nephron blockade with loop and thiazide therapy as an outpatient scheduled daily for more than 7 days prior to admission (Does not include HCTZ < 50mg for blood pressure)
 - Diffuse anasarca with 4+ edema and projected hypervolemia exceeding 40-pounds
 - Severe hepatic impairment (Child-Pugh class C if hepatic impairment is in question)
 - Clinical picture consistent with acute myocardial infarction including troponin rise and fall or ischemic changes on electrocardiogram
 - Site investigator determines the subject is not a good candidate to participate in study at this time

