10.0 Statistical Methods

The full statistical methods are detailed separately in the Statistical Analysis Plan.

The primary analysis model will be the semiparametric proportional odds (PO) ordinal logistic regression model¹⁶ for continuous outcome variables¹⁷. The PO model does not make any distributional assumption for the response variable, is robust to extreme values, and is invariant to transformations of the response variable. It is also extremely efficient when compared to linear regression if normality holds. The Wilcoxon nonparametric two-sample test is a special case of the PO model, but the PO model allows for baseline covariate adjustment. Note that we use covariate adjustment instead of change from baseline so as to not assume that (1) the baseline variable is linearly related to the response variable and (2) the slope of the baseline variable is 1.0.

For binary outcomes we will use the special case of the PO model that is the binary logistic regression model.

For safety analysis of clinical lab variables we use the most powerful and least arbitrary continuous variable analyses and include the empirical cumulative distribution function of post-randomization values of these variables. These continuous analyses will also provide estimates of incidence of such outcomes as hyper- and hypo-kalemia, but will be more sensitive than using only binary responses.

Trial	Experimental agent	Mean decrease in weight (kg) Experimental, (%)	Mean decrease in weight Control, (%)	Within group SD in Experimental Group (kg)
TRUE-AHF ⁸	Ularitide			
RELAX-AHF ¹⁸	Serelaxin	3.6	3.0	4.4
ASCEND-HF ⁹	Nesirtide			
EVEREST ¹⁹	Tolvaptan	3.3	2.7	3.3
TACTICS ²⁰	Tolvaptan	3.7	2.5	4.4
Secrets of HF ²¹	Tolvaptan	3.5	2.4	2.0
ROSE-HF ²²	Nesiritide	3.25	3.5	0.9
ROSE-HF ²²	Dopamine	3.4	3.5	0.9
MEAN		3.5	2.9	2.7

Changes in body weight from admission to discharge in previous literature

Changes in weight by IV 40mg Furosemide Equivalents (FE)

Trial	Experimental agent	Duration (days)	Daily IV loop diuretic dose in FE, mean or median (IQR)*	Median (IQR) decrease in weight (kg)/40mg IV FE	Difference associated with adverse HF outcomes
RELAX-AHF ²³	Serelaxin	5	80	0.42 (1.00, 0.14)	Below median value
DIUR-HF ¹⁴	None	3-5	137 (100, 200)	0.20 (0.281, 0.082)	Below median value
ASCEND-HF ²⁴	Nesiritide	2		0.42 (1.0, 0.05)	Below median value
PROTECT ²⁵	Rolofylline	4	80 (47, 133)	0.38 (0.8, 0.13)	Below median value
EVEREST ^{19,26}	Tolvaptan	4	80	0.30 (0.79, 0.03)	Below median value

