Patients with or without T2DM hospitalized with ADHF will be randomized within 24 hours of evaluation of ADHF in 1:1 ratio to either intervention or structured usual care defined as follows:

- a) **Intervention:** Previous diabetic therapies will be discontinued, and patients will receive protocolized diuretic therapy plus the addition of open label SGLT2 inhibitor therapy with dapagliflozin 10 mg orally once daily for the duration of the study the minimum of 5 days or hospital discharge.
- b) **Structured usual care:** Previous diabetic therapies will be discontinued, and patients will receive protocolized diuretic therapy.

Endpoints

Primary Endpoint:

The primary endpoint is to determine the cumulative change in weight (kg) per 40mg of IV furosemide equivalents from enrollment to the minimum of Day 5 or discharge between 1) protocolized diuretic therapy (structured usual care) and 2) dapagliflozin plus protocolized diuretic therapy guided by urine output.

Sensitivity Endpoint:

The cumulative change in weight (kg) per doubling of the cumulative loop diuretic (analyzed as log2 of the cumulative loop diuretic dose centered on 40mg of IV furosemide equivalent and winsorized at 40mg) from enrollment to Day 5 or discharge between 1) structured usual care and 2) dapagliflozin plus structured usual care

Secondary Endpoints: Comparing differences among the two arms in the following:

a) Incidence of worsening heart failure during hospitalization requiring i) IV inotropic therapy, ii) new admission to an intensive care unit (ICU), iii) new non-invasive positive pressure ventilation with bi-level positive airway pressure, or iv) increase in the IV diuretic protocol intensity by 2 rows after Study Day 1 as adjudicated by the Clinical Event Committee (CEC).

b) Hospital readmission within 30 days of discharge for ADHF or diabetic reasons as adjudicated by the CEC.

Exploratory Endpoints: Comparing differences among the two arms in the following:

- a) NT-proBNP at baseline to discharge adjusted for baseline.
- b) Urine-output based diuretic efficiency defined as the Day 2 24-hour total urine output (ml) per 40/mg of IV furosemide equivalents
 - a. Repeated as per doubling of the cumulative loop diuretic dose (log2 cumulative loop diuretic dose centered at 40mg)
- c) Urine sodium-based diuretic efficiency defined as the Day 2 24-hour total urine sodium excretion (mmol) per 40mg of IV furosemide equivalents (total loop diuretic dose over Day 2)

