- h) The association of length of hospital stay with treatment assignment will be analyzed using the Wilcoxon Rank Sum test

- The association of presence of symptoms of congestion and dyspnea at discharge measured via blinded physician exam and patient reported congestion scores with treatment assignment will be analyzed using the Pearson chi-square test. A proportional odds model will be used to assess the association of discharge congestion score with treatment assignment, adjusting for baseline congestion.
- j) Cumulative incidence of all cause hospital readmission within 30 days of index hospitalization discharge will be graphed by treatment arm treating death as a competing risk. The association of all cause hospital readmission within 30 days of index hospitalization discharge with treatment assignment will be analyzed using the Pearson chi-square test.
- k) The association of number of days at home without hospitalization or emergency room visit during the 30-day follow-up period with treatment assignment will be analyzed using the Wilcoxon Rank Sum test. For purposes of analysis, subjects who died within 30 days of the index hospital discharge will be assigned a value of 0 days at home
- 1) The association of mean serum glucose during therapy with treatment assignment will be analyzed using the Wilcoxon Rank Sum test
- m) Total daily insulin doses (units) utilized per day during therapy will be compared between treatment arms in all comers and in those with diabetes at baseline using a Wilcoxon Rank Sum Test. Total daily insulin doses utilized per day during therapy will be compared to a 'prior to enrollment' utilization using the Wilcoxon Signed Rank Test.
- n) The change in basic metabolic panel laboratory values and hemoglobin from baseline to the end of study will be compared across treatment groups using the Wilcoxon Rank Sum test.
- o) Serum potassium trends over time by treatment assignment will be graphed. Descriptive statistics
 of the daily raw potassium values and kalemic status during hospitalization by treatment group
 will be reported and compared across treatment assignments by Wilcoxon Rank Sum tests and
 Pearson's chi-square tests, respectively.

Safety Analyses:

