 - Dichotomize by median BMI-adjusted NTproBNP [above/below]
- Baseline BMI
 - Continuous
 - Dichotomize by median BMI [above/below]
- Baseline eGFR (calculated using MDRD)
 - Continuous
 - Dichotomize by median eGFR [above/below]
- Baseline weight
 - Continuous
 - Dichotomize by median baseline weight [above/below]
 - Diabetes comorbidity at baseline (Yes or No)
- Left ventricular ejection fraction
 - \circ <= 40 vs > 40
 - \circ < 50 vs >= 50
- Day 1 Fractional excretion of sodium (FENa)-based diuretic efficiency (per 40mg IV furosemide)
 - o Continuous
 - Dichotomize by median FENa [above/below]

References

- Adams KF, Jr., Fonarow GC, Emerman CL, et al. Characteristics and outcomes of patients hospitalized for heart failure in the United States: rationale, design, and preliminary observations from the first 100,000 cases in the Acute Deompensated Heart Failure National Registry (ADHERE). *American heart journal*. 2005; 149(2):209-216.

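### Mean glucose during therapy is tested without baseline adjustment across patients with and without diabetes, which is valid but gives up precision that baseline data already collected could recover

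*Protocol*

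**What the plan says.** **Outcome and test.** Protocol section 2.3 lists "Mean Serum glucose during therapy" without naming an adjustment. SAP Exploratory Analyses l) reads: "The association of mean serum glucose during therapy with treatment assignment will be analyzed using the Wilcoxon Rank Sum test". It names no covariate, stratum or diabetes subset.

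**Population.** SAP, Treatment arms: "Patients with or without T2DM hospitalized with ADHF will be randomized within 24 hours". Under Protocol 5.1 and Appendix B, the insulin algorithms apply to patients with type 2 diabetes. SAP, Randomization, stratifies by site only, so diabetes status is balanced between arms by chance alone.

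**Baseline data.** The Protocol summary's baseline assessments include "standing weight, NT-proBNP, BMP, hemoglobin A1c, spot urine values of sodium, potassium, and creatinine", with no restriction to patients with diabetes. Protocol 3.0 excludes patients with "Serum glucose < 80mg/dl at enrollment", so a glucose value is needed on everyone to establish eligibility. SAP, Descriptive Analysis, lists glucose and HbA1c among the enrollment labs. SAP, Heterogenicity of Treatment Effect, uses baseline diabetes (yes/no), but only as a modifier in the primary model.

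**General approach.** Protocol 10.0 explains its preferred model this way: "The Wilcoxon nonparametric two-sample test is a special case of the PO model, but the PO model allows for baseline covariate adjustment". The SAP applies baseline-adjusted proportional odds (PO) regression to discharge NT-proBNP, Day 2 urinary Na/K ratio and discharge eGFR. Insulin dose, the item after mean glucose, is tested in all patients and again in those with diabetes.

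**The concern.** Diabetes status and starting glucose can be expected to predict glucose over the next few days. Protocol 1.0 points the same way for patients with diabetes: in the sponsor's earlier cohort, admission glucose lay within 50 mg/dl of the chronic average in 66% of them.

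In a pooled rank-sum test, all of that between-patient spread counts as noise. A drug effect that is modest beside the gap between patients with and without diabetes is then harder to see. Adjusting for the baseline values would remove part of the noise at no cost in data. What is at stake is the sharpness of one exploratory glycaemic comparison, not the validity of the trial.

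**Working it through.** **1. The plan's own power figure.** The only power stated, 87%, is for the primary endpoint: 0.1 kg/40 mg difference, SD 0.25, 120 per arm. P = Φ(0.1/(0.25×√2)) = 0.611, and the t-test power is 87.0% (85.3% for a simulated Wilcoxon test). The figure reproduces to within 2 points but says nothing about glucose. No effect, SD or baseline correlation is given for mean glucose, so every glucose input below is assumed.

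**2. General relation.** Let R² be the share of outcome variance explained by the baseline covariates. Adjustment multiplies the noncentrality by 1/√(1−R²), so:

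adjusted power ≈ Φ((1.96 + z)/√(1−R²) − 1.96), where z is the normal quantile of the unadjusted power.

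Example: unadjusted power 30% gives z = −0.524. With R² = 0.5, (1.436 × 1.414) − 1.96 = 0.071, and Φ(0.071) = 53%.

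| Unadjusted power | R² = 0.2 | R² = 0.5 | R² = 0.7 |
|---|---|---|---|
| 30% | 36% | 53% | 75% |
| 50% | 59% | 79% | 95% |
| 80% | 88% | 98% | 99.9% |

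The equivalent sample size is 240/(1−R²): 300, 480 and 800.

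**3. Simulation for the mixed population.** Assumed: 240 patients; glucose with diabetes 175 (SD 45) mg/dl, without 112 (SD 18) mg/dl; effect −20 mg/dl in diabetes only; within-group correlation r between baseline and on-therapy glucose. Unadjusted: Wilcoxon at two-sided 0.05. Adjusted: normal-score regression on arm, baseline glucose and diabetes, as a stand-in for the PO model. HbA1c was left out, so any further gain from it is not counted.

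| Diabetes share | Unadjusted | Adjusted, r = 0.3 | r = 0.5 | r = 0.7 |
|---|---|---|---|---|
| 50% | about 30% | 54% | 60% | 75% |
| 70% | about 57% | 80% | 86% | 95% |

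Repeat runs moved these by a few points, giving 55 to 76% and 78 to 95% as adjusted ranges. Type I error was near 5% for both analyses.

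**4. Other inputs.** A second set (115, SD 20, without diabetes; 180, SD 50, with; smaller effects) pointed the same way. With 40% diabetes, r = 0.3 and effects of 5 mg/dl without and 15 mg/dl with diabetes, power was 35% against 55%. With 10 mg/dl in both groups it was 52% against 80%. With no effect, rejection rates were 4.5 to 5.6% unadjusted and 4.2 to 5.5% adjusted.

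**5. How much SAP n) recovers.** Item n) compares change from baseline in metabolic panel values by Wilcoxon. In the step 3 scenarios, a Wilcoxon test on change in glucose gave:

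| Diabetes share, r | Plain Wilcoxon | Change from baseline | Adjusted (same runs) |
|---|---|---|---|
| 50%, 0.5 | 28% | 47% | 58% |
| 50%, 0.7 | 31% | 67% | 77% |
| 70%, 0.5 | 60% | 74% | 87% |
| 70%, 0.7 | 57% | 89% | 94% |

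These figures favour n), because they treat a single end-of-study value as being as precise as the mean over therapy. At r of 0.2 to 0.3, most of n)'s advantage over the plain test goes.

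**The case against.** **A glucose comparison that uses the baseline is already planned.** Item n) does this, provided the metabolic panel is taken to include glucose, as the SAP's enrollment lab list suggests. Safety analysis c) adds graphs and daily comparisons, and m) tests insulin use separately in patients with diabetes. This stands in part. Item l) would not be read alone, so the documents do not support inferring that a null there would pass as proof of no glycaemic effect. But n) rests on one end-of-study value and was less efficient than adjustment in every scenario in step 5.

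**The plan does not contradict itself here.** A reader might infer that l) breaches the protocol. It does not. Protocol 2.3 attaches baseline adjustment to selected outcomes, mean glucose is not one of them, and Protocol 10.0 defers full methods to the SAP. The adjustment asked for in Protocol 2.4 concerns the glucose safety outcome, so correcting that analysis would not change l).

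**The size rests on assumptions.** This stands. Stopping earlier diabetic therapies and titrating insulin to glucose could weaken the baseline correlation and shrink any difference between arms. Adjustment is no rescue if the effect is small: at −10 mg/dl, adjusted power was only 16 to 43%.

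**Conclusion.** The point holds as one of efficiency. SAP l) is a valid test that leaves unused baseline information already planned for every patient. Under the step 3 assumptions the cost is about 30% against 55 to 76% power with half the patients diabetic, and about 57% against 78 to 95% with 70% diabetic. The documents fix neither the diabetes share nor the correlation.

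A reader might go further and say that most of the attainable power is lost. The documents give nothing to support that, and the arithmetic allows it only in a narrow range. Losing more than half requires R² of at least about 0.57 together with unadjusted power below 50%; at 50% or above it is impossible, since adjusted power cannot exceed 100%. In step 3, 30% against 60% is exactly half, 30% against 75% is more than half, and 57% against 95% is 40% (38/95).

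Priority is low. The outcome is exploratory, no power is stated for it, type I error is sound, and n) covers part of the gap.

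**What to change.** Change SAP Exploratory Analyses l) to a PO model of mean post-randomisation serum glucose on treatment arm, baseline serum glucose (restricted cubic spline, 3 knots, as the primary analysis does for baseline weight), HbA1c and diabetes at baseline (yes/no). Report an arm-by-diabetes estimate as well: if the drug acts mainly in patients with diabetes, a single common odds ratio averages over two different effects. Keep the Wilcoxon result as the unadjusted companion.

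The cost is a line or two of SAP wording, best settled before glucose is compared by arm. No new data are needed, and the SAP's multiple imputation rule for missing covariates, under Main Analysis, already covers missing HbA1c or baseline glucose.
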